10.13. Appendix 13: Abbreviations

The following is a list of abbreviations that may be used in the protocol.

Abbreviation	Term
Abs	absolute
ADA	anti-drug antibodies
ADL	activity/activities of daily living
AE	adverse event
AKI	acute kidney injury
ALP	alkaline phosphatase
ALT	alanine aminotransferase
ANC	absolute neutrophil count
ANCOVA	analysis of covariance
ANOVA	analysis of variance
aPTT	activated partial thromboplastin time
AST	aspartate aminotransferase
AUC	area under the curve
AUC _{inf} (dn)	dose normalized AUC _{inf}
AUC _{inf}	area under the plasma-concentration curve from time 0 extrapolated to infinite time
AUC _{last}	area under the plasma concentration-time profile from time 0 to the time of the last quantifiable concentration (C _{last})
AUC _{last} (dn)	dose normalized AUC _{last}
AV	atrioventricular
AxMP	auxiliary medicinal product
β-hCG	β-human chorionic gonadotropin
BL	baseline
BP	blood pressure
bpm	beats per minute
CDS	Celiac Disease Symptom Diary
CeD	celiac disease
CFR	Code of Federal Regulations
CI	confidence interval
CIOMS	Council for International Organizations of Medical Sciences
CK	creatinase kinase
CKD-EPI	chronic kidney disease epidemiology
C _{last}	last quantifiable concentration
C _{max}	maximum plasma concentration
C _{max} (dn)	dose normalized C _{max}
CO ₂	carbon dioxide (bicarbonate)
COVID-19	coronavirus disease 2019
CL	apparent systemic clearance
CRF	case report form
CRO	contract research organization

Abbreviation	Term
CSR	Clinical Study Report
CT	clinical trial
CTCAE	Common Terminology Criteria for Adverse Events
CTIS	Clinical Trial Information System
CV	cardiovascular
DBP	diastolic blood pressure
DCT	data collection tool
DGP	deamidated gliadin peptide(s)
DILI	drug-induced liver injury
DLT	dose limiting toxicity(ies)
DNA	deoxyribonucleic acid
DSMB	Data Safety Monitoring Board
DU	dispensable unit
EAE	experimental autoimmune encephalomyelitis
EC	ethics committee
ECG	electrocardiogram or electrocardiography
eCrCl	estimated creatinine clearance
eCRF	electronic case report form
EDB	exposure during breastfeeding
EDP	exposure during pregnancy
EFD	embryonic fetal development
EGD	esophagogastroduodenoscopy
eGFR	estimated glomerular filtration rate
eSAE	electronic serious adverse event
ET	early termination
EU	European Union
EudraCT	European Union Drug Regulating Authorities Clinical Trials (European Clinical Trials Database)
FAS	full analysis set
FDA	Food and Drug Administration
FIH	First-in-human
FSH	follicle-stimulating hormone
FU	follow-up
GC	gluten challenge
GCP	Good Clinical Practice
GFD	gluten-free diet
GGT	gamma-glutamyl transferase
GI	gastrointestinal
GLP	good laboratory practice
HBcAb	hepatitis B core antibody
HBsAb	hepatitis B surface antibody
HBsAg	hepatitis B surface antigen
HBV	hepatitis B virus

090177e19fcc12ed\Approved\Approved On: 30-Jan-2024 19:45 (GMT)

Abbreviation	Term
HCV	hepatitis C virus
HCVAb	hepatitis C virus antibody
HIV	human immunodeficiency virus
HLA	human leukocyte antigen
HLA-DQA1 and HLA-DQB1	human leukocyte antigen loci
HLA-DQ2.5	human leukocyte antigen loci encoded by HLA-DQA1*05 and HLA-DQB1*02 (homozygotes or heterozygotes) genotype
HLA-DQ8	human leukocyte antigen serotype with the HLA-DQ serotype group
HR	heart rate
HRT	hormone replacement therapy
hsCRP	high-sensitivity C-reactive protein
IB	Investigator's Brochure
IBS	Irritable Bowel Syndrome
ICD	Informed Consent Document
ICH	International Council for Harmonisation of Technical Requirements for Pharmaceuticals for Human Use
ID	Identification
IEL	intraepithelial lymphocytes
IgA	immunoglobulin A
IgG	immunoglobulin G
IL-2	interleukin-2
IMP	investigational medicinal product
IND	Investigational New Drug
INR	international normalized ratio
IPAL	Investigational Product Accountability Log
IPM	investigational product manual
IRB	Institutional Review Board
IRR	infusion-related reaction
IRT	Interactive Response Technology
ISF	Investigator Site File
IV	intravenous(ly)
k_{el}	elimination rate constant
KDIGO	Kidney Disease: Improving Global Outcomes
LBBB	left bundle branch block
LFT	liver function test
LSM	least-squares mean
MAD	multiple ascending dose
MedDRA	Medical Dictionary for Regulatory Activities
MHC	major histocompatibility complex
MQI	medically qualified individual
MTD	maximum tolerated dose
N/A	Not Applicable

090177e19fcc12ed\Approved\Approved On: 30-Jan-2024 19:45 (GMT)

Abbreviation	Term
NCI	National Cancer Institute
NIMP	noninvestigational medicinal product
NOAEL	no observed adverse effect level
NTD	non-tolerated dose
OH	orthostatic hypotension
OTC	over the counter
PBMC	peripheral blood mononuclear cell
PBO	placebo
PD	pharmacodynamic(s)
PGIC	Patient Global Impression of Change
PGIS	Patient Global Impression of Severity
PI	Primary Investigator
PK	pharmacokinetic(s)
PO	by mouth; oral(ly)
PR	pulse rate
PRO	patient reported outcomes
PSSA	Pfizer's Serious Adverse Event Submission Assistant
PT	Preferred Term; prothrombin time
QTc	corrected QT interval
QTcF	QTc corrected using Fridericia's formula
qual	qualitative
Rand.	Randomization
RBC	red blood cell
RNA	ribonucleic acid
RR	respiratory rate
SAD	single ascending dose
SAE	serious adverse event
SAP	Statistical Analysis Plan
SARS-CoV-2	severe acute respiratory syndrome coronavirus 2
SBP	systolic blood pressure
Scr	serum creatinine
Scys	serum cystatin C
SM	safety margin
SoA	schedule of activities
SOC	System Organ Class
SOP	standard operating procedure
SRSD	Single Reference Safety Document
SUSAR	Suspected Unexpected Serious Adverse Reactions
t _{1/2}	terminal phase half-life
T bili	total bilirubin
TEAE	treatment-emergent adverse events
TPN	total parenteral nutrition
tTG	transglutaminase

090177e19fcc12ed\Approved\Approved On: 30-Jan-2024 19:45 (GMT)

Abbreviation	Term
T _{max}	time to reach C _{max}
ULN	upper limit of normal
US	United States
UTI	urinary tract infection
V	apparent volume of distribution
WBC	white blood cell
WOCBP	woman/women of childbearing potential

1. VERSION HISTORY

This Statistical Analysis Plan (SAP) for study KAN-101-02 Part A is based on the protocol amendment dated 21Jun2023.

Table 1. Summary of Changes

Version/Date	Associated Protocol Amendment	Rationale	Specific Changes
1 28OCT2022	Original 31Aug2022	Not Applicable (N/A)	N/A
2 10Jul2023	Amendment 1 21Jun2023	Protocol Amended	In Section 2.3, 6 mg/kg KAN 101 (cohort 3) was removed.
3 13Jun2025	Amendment 3 30Jan2024	Protocol Amended Study termination	Section 2, Part C was added. Section 6.3, the tertiary/exploratory endpoints will not be measured/reported.

2. INTRODUCTION

Study KAN-101-02 is a 3-part, multicenter Phase 1b/2 study of KAN-101 in participants with celiac disease (CeD) on a gluten-free diet (GFD). The 3 parts include: Part A – Open-label, multiple ascending dose (MAD); Part B – Double-blind, placebo (PBO)-controlled, parallel design; Part C – Double-blind, placebo (PBO)-controlled, parallel design.

This SAP provides the detailed methodology for summary and statistical analyses of the data collected in study KAN-101-02 Part A. This document may modify the plans outlined in the protocol; however, any major modifications of the primary endpoint definition or its analysis will also be reflected in a protocol amendment.

2.1. Modifications to the Analysis Plan Described in the Protocol

“Entered” analysis set is added to [Section 4](#), it is not in the protocol.

2.2. Study Objectives, Endpoints, and Estimands

Study Part A objectives and corresponding endpoints are provided in the [Table 2](#) below. Part A is open label. The primary objective is to evaluate the safety of KAN-101. There is no hypothesis testing. Estimands are not applicable for Part A.

Table 2. Objectives and Endpoints

Objectives	Endpoints
Primary:	

 Assess the safety and tolerability of KAN-101 in participants with CeD. 	
 Incidence and severity of treatment-emergent adverse events (TEAEs) as assessed by the Common Terminology Criteria for Adverse Events (CTCAE).
Secondary:	

 Assess the pharmacokinetics (PK) of multiple doses of KAN-101 in participants with CeD. 	
 KAN-101 plasma exposure as data permit: AUC_{inf}, AUC_{last}, C_{max}, T_{max} and t_½.
Tertiary/Exploratory:	

 To further characterize the PK profile of KAN-101 following multiple doses in participants with CeD. To evaluate the immunogenicity of KAN-101. Examine the biomarker response (interleukin-2 [IL-2]) in peripheral blood following gluten challenge (GC) and after dosing. 	
 KAN-101 PK parameters, as data permit: AUC_{inf} (dn), AUC_{last} (dn), C_{max}(dn), CL, V. Incidence of development of anti-drug antibodies (ADA) during the study. Change in magnitude of IL-2 response pre-and-post GC in peripheral blood at Day 15.

2.3. Study Design

Study KAN-101-02 is a 3-part, multicenter Phase 1b/2 study of KAN-101 in participants with CeD on GFD. The 3 parts include:

- **Part A** – Open-label, multiple ascending dose
- **Part B** – Double-blind, PBO-controlled, parallel design
- **Part C** – Double-blind, PBO-controlled, parallel design

Part A is a Phase 1b, open-label, MAD 3+3 study design to assess the safety, tolerability and PK of KAN-101 in adult participants (18 to 70 years inclusive) with histology-confirmed CeD. Up to 6 participants who meet study inclusion/exclusion criteria may be randomized in the study.

Eligible participants will be administered IV study intervention on Day 1, Day 4, and Day 7. The dose cohorts planned for Part A are:

- 1.2 mg/kg (Cohort 1)
- 3.0 mg/kg (Cohort 2)

Participants who withdraw from the study may be replaced at the discretion of the sponsor. A replacement subject will receive the same treatment as the withdrawn participant. No

[figure not shown]
participant with a dose limiting toxicity (DLT) will be replaced. Each dose group (cohort) may have 3-6 participants.

Based on emerging data from previous and ongoing cohorts, doses planned may be repeated, modified and other doses may be explored in additional cohorts. If the exposures in the subsequent dose are projected to exceed the exposure limits pre-specified, that dose will not be explored.

All participants administered KAN-101 will return to the clinic on Day 15 to receive a 1-day 9g oral GC to assess exploratory endpoints (plasma IL-2 biomarker response to gluten and collect symptom information).

For Part A, a data safety monitoring board (DSMB) will review cumulative safety data through the dose escalation safety review period by cohort before opening a higher dose cohort. Initiation of the next dose cohort will commence once all participants in a cohort reach Day 15 prior to the GC, and upon acceptable safety review by DSMB and approval from sponsor.

Figure 1. Part A Study Design Schema

* Depending on safety and tolerability, each group may enroll 3 additional participants to establish the MTD.

3. ENDPOINTS AND BASELINE VARIABLES: DEFINITIONS AND CONVENTIONS

3.1. Primary Endpoint

- Incidence and severity of TEAEs as assessed by CTCAE.

An adverse event (AE) is considered TEAE to a given treatment if the event start date is on or after the treatment period start date and before end of study.

The CTCAE (V5.0) displays Grades 1 through Grade 5 with unique clinical descriptions of severity for each AE based on below general guideline:

- **Grade 1:** Mild; asymptomatic or mild symptoms; clinical or diagnostic observations only; intervention not indicated.
- **Grade 2:** Moderate; minimal, local or noninvasive intervention indicated; limiting age appropriate instrumental activities of daily living (ADL).
- **Grade 3:** Severe or medically significant but not immediately life-threatening; hospitalization or prolongation of hospitalization indicated; disabling; limiting selfcare ADL.
- **Grade 4:** Life-threatening consequences; urgent intervention indicated.
- **Grade 5:** Death related to AE.

3.2. Secondary Endpoints

- KAN-101 plasma exposure as data permit: AUC_{inf} , AUC_{last} , C_{max} , T_{max} and $t_{1/2}$.

Parameter	Definition	Method of Determination
AUC_{last}	Area under the plasma concentration-time profile from time 0 to the time of the last quantifiable concentration (C _{last})	Linear/Log trapezoidal method
AUC_{inf}	Area under the plasma concentration-time profile from time 0 extrapolated to infinite time	$AUC_{last} + (C_{last}/K_{el})$, where C _{last} is the predicted plasma concentration at the last quantifiable time point estimated from the log-linear regression analysis

Parameter	Definition	Method of Determination
C_{max}	Maximum plasma concentration	Observed directly from data
T_{max}	Time to first occurrence of C_{max}	
$t_{1/2}^a$	Terminal elimination half-life	$\text{Log}_e(2)/K_{el}$, where K_{el} is the terminal Phase rate constant calculated by a linear regression of the loglinear - concentration time- curve. Only those data points judged to describe the terminal log-linear decline will be used in the regression

a. If data permits.

3.3. Exploratory Endpoints

- KAN-101 PK parameters, as data permit: $AUC_{last}(dn)$, $AUC_{inf}(dn)$, $C_{max}(dn)$, CL, V.

Parameter	Definition	Method of Determination
$AUC_{last}(dn)$	Dose normalized AUC_{last}	AUC_{last}/Dose
$AUC_{inf}(dn)$	Dose normalized AUC_{inf}	AUC_{inf}/Dose
$C_{max}(dn)$	Dose normalized C_{max}	C_{max}/Dose
CL^a	Apparent systemic clearance	Dose/AUC_{last}
V^a	Apparent volume of distribution following IV dosing	$\text{Dose}/AUC_{inf} \times K_{el}$

a. If data permits.

- Incidence of development of ADA during the study.
- Change in magnitude of IL-2 response pre-and-post GC in peripheral blood at Day 15.

IL-2 response to GC is IL-2 post-GC at Day 15 – IL-2 pre-GC at Day 15.

3.4. Demographic and Baseline Variables

Demographic and baseline characteristics include:

- Age
- Sex
- Race
- Ethnicity
- Height (in cm)
- Weight (in kg)
- Body Mass Index
- Duration of CeD
- Duration of GFD
- HLA genotype
- CeD Serology at diagnosis
- Histology at diagnosis

3.5. Safety Endpoints

Safety will be assessed by medical history, vital signs, clinical laboratory tests, and the spontaneous reporting of AEs, in all participants who received any portion of study intervention. Unscheduled safety assessments may be performed at any time during the study to assess any perceived safety concerns. Investigators and Clinicians will review individual participant data throughout the conduct of the study to ensure participants' well-being.

3.5.1. Adverse Events

Incidence and severity of TEAEs is the primary endpoint of Part A. See [Section 3.1](#).

3.5.2. Safety Laboratory Data

Safety laboratory testing will be performed at Screening, Days 1, 4, 7, 15, 28, or early termination (ET) visit. The details are listed in below table.

Hematology	Chemistry	Urinalysis	Other
Hemoglobin Hematocrit RBC count Platelet count WBC count Total neutrophils (Abs, %) Eosinophils (Abs, %) Monocytes (Abs, %) Basophils (Abs, %) Lymphocytes (Abs, %) PT aPTT ^a INR ^a	Urea and creatinine eGFR Glucose (fasting) Calcium Sodium Potassium Chloride Total CO ₂ (bicarbonate) AST, ALT Total and direct bilirubin Alkaline phosphatase Uric acid Albumin Total protein Magnesium Amylase Lipase Phosphorus	Local dipstick: pH Glucose (qual) Protein (qual) Blood (qual) Ketones Nitrites Leukocyte esterase Laboratory: Microscopy and culture ^b	At screening: 
 • FSH^c • Pregnancy test (β-hCG)^d • Hepatitis B surface antigen and HbcAb, HBsAb and HBV DNA as reflex tests • Hepatitis C antibody and HCV RNA as reflex test • HIV • HLA DQ2.5 and HLA DQ8 testing^e • tTG and DGP IgA/IgG^f

- aPTT and INR tests are performed in Part A only.
- Only if UTI is suspected and urine dipstick is positive for nitrites or leukocyte esterase or both.
- For confirmation of postmenopausal status only.
- A serum pregnancy test is required at screening. Following screening, local urine testing will be standard for the protocol unless serum testing is required by local regulation or IRB/EC. Serum or urine β-hCG for female participants of childbearing potential.
- For re-screening, the HLA does not need to be repeated and CeD serology (the tTG and DGP antibody tests) should only be repeated if >3 months have elapsed from end assessment.
- For tTG, a result of <2 x ULN will be considered negative or weak positive. For DGP, a result of <30 U/mL will be considered negative or weak positive.

3.5.3. Vital Signs

Vital signs will be assessed at Screening, Days 1, 4, 7, 15, 28, or ET visit.

4. ANALYSIS SETS

For purposes of analysis, the following analysis sets are defined for Part A:

Analysis Set	Description
Entered	All participants who sign the informed consent document (ICD).
Enrolled	All entered participants who are assigned to study intervention in Part A.
Full analysis set (FAS)	All participants who receive any portion of study intervention in Part A.
Safety analysis set (SAS)	All participants who receive any portion of study intervention in Part A. It is the same as FAS.
PK analysis set (PKAS)	All participants who receive any portion of study intervention and have at least one concentration value in Part A.

5. GENERAL METHODOLOGY AND CONVENTIONS

5.1. Hypotheses and Decision Rules

Part A is open label. There is no hypotheses and decision rules.

5.2. General Methods

In general, count and percent will be presented for categorical variables. Number of observations, mean, standard deviation (SD), minimum (min), median, and maximum (max) will be presented for continuous variables. The coefficient of variation (CV), geometric mean (GM), geometric mean ratio (GMR) will also be included, where appropriate. Graphics may be used to present the data. All summaries will be performed by dose group.

5.3. Methods to Manage Missing Data

Missing values will not be imputed for safety, efficacy and PK endpoints. If a PK concentration value is below Lower Limit of Quantification (LLOQ), that concentration value will be treated as 0 for all analysis. For IL-2, values below LLOQ will be treated as $\frac{1}{2}$ LLOQ.

6. ANALYSES AND SUMMARIES

6.1. Primary Endpoint

The primary endpoint for Part A is incidence and severity of TEAEs. Adverse events will be summarized for SAS according to Sponsor's reporting standards for

- TEAEs
- Serious AEs (SAEs)

TEAEs will be summarized overall and Day 1 to Day 15 prior GC by dose group by the number of participants reporting any TEAE, system organ class (SOC), preferred term (PT), severity, relationship to investigational product. CTCAE is used to grade the severity of AEs. TEAEs related to GC and infusion-related reactions (IRR) will also be summarized separately.

SAEs will be summarized by SOC and PT, and individual SAEs will be listed by participant.

A list of subjects who prematurely discontinue from the study due to an AE will be provided as well.

6.2. Secondary Endpoints

6.2.1. PK concentration

PK concentration will be descriptively summarized by dose group and nominal timepoints with number of observations, mean, SD, min, median, max for PKAS. Line plot will be provided by dose group for mean and individual concentration-time profiles using linear and semi-log scale, .

6.2.2. PK parameters

PK parameters listed in [Section 3.2](#) (AUC_{inf} , AUC_{last} , C_{max} , T_{max} , and $t_{1/2}$) will be descriptively summarized by dose group with number of observations, mean, SD, min, median, and max, GM, and %CV for PKAS. No GM and %CV for T_{max} .

6.3. Exploratory Endpoints

The tertiary/exploratory endpoints will not be measured/reported due to study termination.

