4.1.2. Part B: Phase 2, Double-Blind, Placebo-Controlled Study

Part B is a Phase 2, double-blind, PBO-controlled, parallel design study to characterize the biomarker response (plasma IL-2; primary endpoint) in peripheral blood following GC, Safety, tolerability, and PK of KAN-101 in adult participants (18 to 70 years of age inclusive) with histology-confirmed CeD will also be analyzed. 16 participants (approximately 4 participants per dose group) will be randomized 1:1:1:1 and stratified by participation in biopsy substudy to the following treatment groups:

- PBO (Group 1)
- 0.6 mg/kg (Group 2)
- 1.2 mg/kg (Group 3)
- 3.0 mg/kg (Group 4)

Initiation of Part B will occur following the DSMB review of available safety and PK data from Part A and the sponsor's approval.

Part B comprises 4 periods and 1 sub-study:

- **Screening period:** ≤ 28 days
- **Run-in period:** 21 days
 - Eligible participants will undergo a 1-day 9g GC on first day of run-in period (21 days before administration of first dose of study drug) to confirm symptomatic response to oral GC (see [Section 8.2.1](#)).
 - Non-responders (participants with asymptomatic response to GC) will be screen-failed from the study.
 - Symptomatic responders eligible to participate in the study will be randomized and will proceed to the Treatment period.
- **Treatment period:** 7 days
 - Symptomatic responders to the run-in GC will be randomized 1:1:1:1 to one of the 4 Treatment groups and administered study intervention IV for 3 administrations (1 administration every 3 days starting at Day 1).

Post infusion, participants will be monitored in the clinic for 4 hours for infusion-related reactions (see [Appendix 9](#)).

- **Observation/follow-up period:** 358 days
 - **Post-dosing GC on Day 15:** All participants will return to the clinic on Day 15 to receive a 1-day 9 g oral GC to assess plasma IL-2 biomarker response (primary endpoint) to gluten and collect symptom information.
 - **Post-dosing GC at Weeks 12, 24, and 36:** All participants will return to the clinic to receive a 1-day 9 g oral GC to assess plasma IL-2 biomarker response to gluten and collect symptom information (exploratory endpoints).
 - **Follow-up visits: on Day 28 and Week 52.**
- **Biopsy Substudy** (applicable sites only)

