4.2. Scientific Rationale for Study Design

In KAN-101-01 study, participants treated with 0.15 mg/kg, 0.3 mg/kg and 0.6 mg/kg of KAN-101 exhibited T-cell tolerance to gliadin by demonstrating minimal change or a decrease in the gliadin-specific T-cell response to GC compared to participants in the placebo

who exhibited an increase in the gliadin-specific T-cell response following GC. In addition, participants treated with 0.6 mg/kg KAN-101 exhibited lower median interleukin-2 (IL-2) levels after GC compared to the IL-2 levels in Placebo or 0.15 mg/kg and 0.3 mg/kg KAN-101 groups. Overall, KAN-101 demonstrated an acceptable safety and tolerability profile in both Part A and Part B of the study at all doses tested. There were no deaths, SAEs, Grade 3 TEAEs, or DLTs observed; therefore, no MTD was determined in this study. With expected efficacy dose of 1.2 mg/kg or over, higher doses may be explored in future studies. Further details are provided in the KAN-101 IB.

In KAN-101-01 and non-clinical models, T-cell tolerance induction was observed as early as 1 week after drug administration in celiac patients, supporting the timing of the primary endpoint assessment and the safety review period.

In the previous protocol for this study, 1.2 mg/kg, 3.0 mg/kg and 6.0 mg/kg KAN-101 were planned to be evaluated in a MAD 3+3 design (Part A). Based upon emerging data from Part A, the protocol has been amended to proceed to Part B following completion of Part A 3.0 mg/kg dose cohort. The decision not to test 6.0 mg/kg was not due to any safety concerns or exposures which exceeded the NOAEL. Part B evaluated 0.6 mg/kg, 1.2 mg/kg, and 3.0 mg/kg in a dose-ranging design (Part B) in CeD participants on GFD

Sixteen participants were randomized at which time, study was paused and ad-hoc DSMB was convened to assess emerging safety data.

After review of emerging data by DSMB, Part B was closed due to concerns for sensitization by screening GC, potentially leading to higher frequency and severity of AEs observed after dosing with KAN-101/PBO. The study remains blinded.

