1. VERSION HISTORY

This Statistical Analysis Plan (SAP) for study KAN-101-02 Part B is based on the protocol amendment dated 30Jan2024.

Table 1. Summary of Changes

Version/Date	Associated Protocol Amendment	Rationale	Specific Changes
1 28OCT2022	Original 31Aug2022	Not Applicable (N/A)	N/A
2 10Jul2023	Amendment 1 21Jun2023	Protocol amended	In Section 2.3, study drug arms are defined as 0.6 mg/kg, 1.2 mg/kg, and 3.0 mg/kg as active study drug arms and placebo in Part B
28Feb2024	Amendment 3 30Jan2024	Protocol amended	
Section 2 and Section 2.3, Part C was added, Figure 1 was updated.
 
Section 2.2 Table 2 and Section 2.2.1, estimand 1 was changed to treatment policy, estimand 2 was removed.
 
Section 3.1 and Section 3.3, some editorial changes.
 
Section 5.1 was updated to reflect that there is no hypothesis testing for Part B.
 
Section 5.1 was removed. No analysis for continuous endpoints.
 
Section 6.1 was updated to reflect that only descriptive summary will be performed for the primary endpoint.

Table 1. Summary of Changes

Version/Date	Associated Protocol Amendment	Rationale	Specific Changes
			
Main analysis and sensitivity analysis were removed for the primary endpoint.
 
Sections 6.3.3, 6.3.4, 6.3.5 (old Sections 6.4.3, 6.4.4, 6.4.5 in version 2), analysis was removed.
 
Section 6.6 (old Section 6.7), listings and/or summaries for participants impacted by COVID-19 were removed.
 
Section 7, Interim analysis was removed.
 
Appendix 1, Analysis related items were removed.
 
Appendix 2.1, analysis windows were added for Immunogenicity data (Table 6).

13Jun2025	Amendment 3 30Jan2024	Study termination	Section 6.3 and Appendix 1, the exploratory endpoints (except section 6.3.2 Incidence of development of ADA during the study) will not be measured/reported.

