6.3.2. Incidence of Development of ADA During the Study

Participants positive for ADA (screening, confirmatory, specificity and titer) will be summarized by treatment group and timepoint with number and percent for SAS.

6.3.3. Change in Magnitude of IL-2 Response pre- and post-GC in Peripheral Blood from Baseline to GC at Weeks 12, 24, and 36

These endpoints will not be measured/reported due to study termination.

6.3.4. Change in Magnitude of IL-2 Response pre- and post-GC in Peripheral Blood from GC at Day 15 to GC at Weeks 12, 24, and 36

These endpoints will not be measured/reported due to study termination.

6.3.5. Change in circulating levels of various biomarkers from pre-dose to post-dose on Day 1, 4, and 7

These endpoints will not be measured/reported due to study termination.

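### SAP Part A drops the ADA summary because of study termination, a reason that does not fit Part A and that did not stop SAPs B and C from keeping it

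*SAP*

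**What the plan says.** SAP Part A lists immunogenicity as an objective in Table 2 of Section 2.2, with the endpoint "Incidence of development of anti-drug antibodies (ADA) during the study", and Section 3.3 repeats it as an exploratory endpoint ("Incidence of development of ADA during the study"). Section 6.3 then removes every endpoint in that class: "The tertiary/exploratory endpoints will not be measured/reported due to study termination". The version history dates this to version 3, 13 June 2025, and makes no exception: "Section 6.3, the tertiary/exploratory endpoints will not be measured/reported".

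SAP Part B carries an entry of the same date, also citing termination, but it carves ADA out: "the exploratory endpoints (except section 6.3.2 Incidence of development of ADA during the study) will not be measured/reported". Its Section 6.3.2 keeps the analysis: "Participants positive for ADA (screening, confirmatory, specificity and titer) will be summarized by treatment group and timepoint with number and percent for SAS". SAP Part C version 4, again of 13 June 2025, names the cancelled sections as 6.3.1, 6.3.3 to 6.3.5 and 6.3.7. Section 6.3.2 is not among them, and it holds the same ADA summary as SAP B.

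Protocol 9.3.4 lists ADA incidence among the exploratory analyses for Part A and refers to 9.3.7, which promises a descriptive summary of immunogenicity.

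**The concern.** Two things do not fit together. First, one event on one date leads to opposite treatment of the same endpoint: ADA survives in the two longer parts and disappears from the shortest. Second, Part A is the part least likely to have been cut short. Its participants finish at Day 28, and Part B waited for it: "Initiation of Part B will occur following the DSMB review of available safety and PK data from Part A".

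At stake is a small piece of safety-relevant description. The risk table in Protocol 2.3.1 names hypersensitivity as a potential risk of KAN-101, and Part A's primary purpose is safety and tolerability. As written, SAP A states an immunogenicity objective and then has no analysis that answers it.

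**Working it through.** The plan gives no figure on this point to reproduce. The check compares the texts, then dates, then size.

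**1. The three SAPs side by side**

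| | Part A | Part B | Part C |
|---|---|---|---|
| ADA listed as exploratory endpoint | Yes (2.2, 3.3) | Yes (2.2, 3.3) | Yes (2.2, 3.3) |
| Date of termination-driven revision | 13 Jun 2025 | 13 Jun 2025 | 13 Jun 2025 |
| ADA analysis after revision | None (6.3) | Kept (6.3.2) | Kept (6.3.2) |
| Scheduled ADA samples | Days 1, 7, 28 (or ET) | Days 1, 7, 28; Weeks 12, 24, 36, 52 (or ET) | As Part B |

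**2. Could termination have prevented Part A sampling?**

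- Last scheduled Part A visit: Day 28, window Day 25 to Day 31 (Protocol 1.3.1). It is also the last ADA sample.
- Protocol 4.2, in the version approved 30 January 2024, says of the last planned cohort that "the protocol has been amended to proceed to Part B following completion of Part A 3.0 mg/kg dose cohort". It also reports that sixteen Part B participants had been randomized and that Part B had been closed.
- If cohort completion is read as reaching Day 15, which is the escalation criterion, the last Part A visit falls at most 31 − 15 = 16 days later. Each Part B participant had a run-in challenge at least 21 days before first dose.
- The termination date is not given. SAP C version 3 (13 December 2024) does not mention termination; the revisions of 13 June 2025 are the first to do so.
- 30 January to 13 December 2024: day 348 − day 30 = 318 days. 13 December 2024 to 13 June 2025: 182 days. Total: 318 + 182 = 500 days.

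Part A sampling therefore appears to have ended before 30 January 2024, and the SAP change came 500 days after that date. This is an inference from sequence and dates, but a strong one.

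**3. Size**

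- Planned Part A size: 6 to 12, all on KAN-101 (Protocol 9.5). SAP A 2.3 says up to 6 in total but also 3 to 6 in each of two cohorts. Protocol 4.1.1 says up to 18. The range 6 to 12 is used here.
- Scheduled ADA samples: 6 × 3 = 18 to 12 × 3 = 36.

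**4. How much the table could show**

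With no positives among n, the two-sided 95% Clopper-Pearson upper limit is 1 − 0.025^(1/n):

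- n = 3 (smallest cohort): 71%
- n = 6: 45.9%
- n = 12: 26.5%

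The chance of at least one positive is 1 − (1 − p)^n. The documents give no ADA rate. For an assumed p of 10% to 30% this is 47% to 88% at n = 6 and 72% to 99% at n = 12. The table would be descriptive only, but a positive finding would have a reasonable chance of appearing in it.

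**The case against.** The strongest reply is that the sponsor was free to do this. ADA is exploratory in every part. Protocol 9.3.4 says exploratory results serve internal purposes and may be left out of the study report. The opening of Protocol 9 lets the SAP change the plan and asks for an amendment only for major changes to primary endpoints. That stands: a reader might infer a protocol breach, and there is none. But the same latitude covers Parts B and C, where ADA was kept, so it does not explain the difference, and it is not the reason SAP A gives.

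A second reply is that samples drawn are not samples assayed, and termination can halt laboratory or reporting work. This also stands as a possibility. The documents are silent on assay status. If that is what happened, SAP A should say so.

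Third, a reader might infer that immunogenicity information is lost. The documents do not support that. Both Part A doses, 1.2 and 3.0 mg/kg, are also studied in Parts B and C, with a planned 2 × (4 + 26) = 60 participants, concurrent placebo and ADA sampling to Week 52. Actual numbers in the terminated study are not given.

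Fourth, a reader might suspect selective reporting. SAP A drops all exploratory endpoints alike, no result is known, and retention varies elsewhere too: SAP B drops patient-reported outcomes while SAP C keeps them to Week 12. Leaving cancelled endpoints in the objectives table is also common to all three SAPs. An oversight is a sufficient explanation.

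Finally, Part A has denser PK sampling, 8 points per profile against 4 in Parts B and C, which invites a request for an ADA-by-PK listing. No document plans such an analysis. In Part A, only the Day 7 pre-dose ADA sample is both after exposure and scheduled alongside a PK profile. The request would go beyond consistency with SAPs B and C.

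**Conclusion.** The point holds as a minor one. SAP A removes the ADA summary for a reason that does not fit a 28-day part completed before Part B, while the other two SAPs keep it on the same date under the same heading of termination. The consequence is a stated objective left unreported for a planned 6 to 12 KAN-101 participants. No power, error rate or primary result is affected: adverse events, infusion-related reactions and PK in Part A are still summarized (SAP A 6.1 and 6.2). SAP A 2.1, which lists changes from the protocol, mentions only the added analysis set and not this removal.

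The conclusion rests on planned enrolment and on the inferred timing of Part A. It would change only if there were a Part A-specific obstacle, such as samples that cannot be assayed, which the documents do not mention.

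**What to change.** In SAP A 6.3, make the exception that SAP B makes and insert the summary used in Section 6.3.2 of SAPs B and C: number and percent of ADA-positive participants by dose group and timepoint, safety analysis set, at Day 1 pre-dose, Day 7 pre-dose and Day 28 or early termination. Amend the version history to match. SAP A has no immunogenicity window table, so either report by nominal visit or add a short one modelled on Table 6 of SAP C.

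The cost is one small descriptive table and, if not already done, assay of the 18 to 36 samples the schedule provides for. If the samples cannot be assayed, state that reason in 6.3 and record the omission as a departure in 2.1.
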